8.8 Treatment of Overdose

There are no known antidotes for overdoses of PF-07901801, PLD or doxorubicin, the active component of PLD. In the event of an overdose of PF-07901801 or PLD, discontinuation of

treatment may not have immediate therapeutic effect. In the event of a known or suspected overdose, the participant should be monitored with appropriate hematology and clinical chemistry and should receive supportive therapy, as necessary.

The PLD Full Prescribing Information reports that overdosage with doxorubicin hydrochloride causes increased risk of severe mucosities, leukopenia and thrombocytopenia. Treatment of a severely myelosuppressed participant require hospitalization, anti-microbials, platelet transfusions and symptomatic treatment of mucositis. Use of hematopoietic growth factor (G-CSF, GM-CSF) may be considered.

Doxorubicin hydrochloride liposome injection Prescribing Information carries a warning that myocardial damage, include left ventricular failure, can occur. Thus, dexrazoxane may be considered for cardioprotection in participants who have received an excess of doxorubicin. The Prescribing Information also carries a warning that serious, life-threatening, and fatal infusion-related reactions can occur but does not mandate prophylaxis for such reactions. At the discretion of the investigator and in accordance with institutional guidelines, the investigator may implement prophylaxis.

Decisions regarding dose interruptions or modifications for PF-07901801 and/or PLD in the case of a suspected overdose will be made by the investigator in consultation with the sponsor medical monitor based on the clinical evaluation of the participant.

Information regarding the quantity of the excess dose as well as the duration of the overdosing should be documented in the appropriate eCRF.

9 MONITORING AND MANAGEMENT OF EXPECTED OR POTENTIAL ADVERSE EVENTS

Participant safety will be monitored throughout the study and supportive measures consistent with optimal participant care according to institutional standards should be provided throughout the study. Emergency resuscitation equipment and medications should be readily available. Additional supportive measures should also be available and may include epinephrine, antihistamines, corticosteroids, IV fluids, vasopressors, oxygen, bronchodilators and acetaminophen.

Adverse events observed, mentioned or spontaneously reported by the participant will be documented. The investigator will be responsible for monitoring the safety of participants and for alerting the sponsor or its designee of any event that seems unusual, even events considered an unanticipated benefit to the participant. The investigator is responsible for appropriate medical care of participants during the study and for adverse events that are serious in nature, considered related or unrelated to the study intervention or that cause the participant to discontinue. Laboratory abnormalities and adverse events will be graded according to NCI CTCAE version 5.0.

In the following section, guidelines are presented for management of adverse events attributed to PF-07901801 (Section 9.1) or PLD (Section 9.2) and management of adverse events when attribution to neither agent is possible in the opinion of the investigator (Section 9.3).

9.1 Management of Adverse Events Associated with PF-07901801

Except in the case of proteinuria, asymptomatic laboratory abnormalities should not result in dose interruptions, modifications, or discontinuation of study therapy unless determined by the investigator to be clinically significant or life-threatening.

9.1.1 PF-07901801 Treatment Interruptions

Treatment with PF-07901801 may be interrupted for up to 56 days for toxicity assessed as related to treatment with PF-07901801; treatment may be interrupted for up to 28 days for reasons unrelated to toxicity if the participant is receiving disease control and after discussion with the sponsor medical monitor. Treatment may be re-instated after discussion with the medical monitor. In general, if an interruption of more than 56 days is required due to adverse events, PF-07901801 will be permanently discontinued; however, if in the judgment of the investigator, the participant is likely to derive disease control from PF-07901801 after a hold of more than 56 days, study drug may be re-started with the approval of the sponsor medical monitor. The infusion duration may be increased and/or other precautionary measures instituted after discussion with the sponsor medical monitor, but the PF-07901801 dose level does not require modification when administration is re-started. Longer interruptions may be acceptable on a participant -by- participant basis at the discretion of the investigator after discussion with the sponsor medical monitor.

9.1.2 PF-07901801 Re-Treatment Guidelines

The parameters described in Table 14 should be met for re-treatment with PF-07901801 on any study day.

Table 14. Requirements for Re-Treatment with PF-07901801

Parameter	Criterion
ANC	$\geq 1.0 \times 10^9 / L$
Platelet Count	$\geq 75 \times 10^9 / L$
Bilirubin	≤1.5 × ULN (≤2 x ULN if hyperbilirubinemia is due to Gilbert's syndrome)
AST, ALT	\leq 3 × ULN (<5 × ULN if liver metastases)
Treatment-Related Adverse Event	NCI CTCAE Grade <2 or baseline level (except for alopecia)

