9.1.6 Management of Other Adverse Events Related to PF-07901801 Administration

PF-07901801 dose adjustments based on the occurrence of other treatment-related adverse events are described in Table 18.

Table 18. Management of other Treatment-Related Adverse Events

Severity of Event	Management Guidelines	
C 1 1	Maintain PF-07901801 dose level	
Grade 1	Provide treatment to control symptoms if applicable	
C 1- 2 (4-111-)	Maintain PF-07901801 dose level	
Grade 2 (tolerable)	Provide treatment to control symptoms if applicable	
Grade 2 (intolerable)	• Hold administration of PF-07901801 until the adverse event recovers to Grade ≤1 or to baseline level, then resume treatment with PF-07901801	
Grade 3	 Hold administration of PF-07901801 until the adverse event recovers to Grade ≤1 or to baseline level, then resume treatment with PF- 07901801 	
Grade 4	Discontinue PF-07901801 unless participant is receiving disease control, adverse event recovers to baseline level and treating physician recommends continuation of treatment at a lower dose level or under a modified schedule	

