9.2.2 PLD Re-Treatment Guidelines

The laboratory parameters described in Table 21 should be met for re-treatment with PLD (i.e., initiation of a new cycle).

Table 21. Requirements for Re-Treatment with PLD

Parameter	Criterion
ANC	$\geq 1.5 \times 10^9 / L$
Platelet Count	\geq 75 × 10 ⁹ /L
Bilirubin	$\leq 1.5 \times \text{ULN}$ ($\leq 2 \times \text{ULN}$ if hyperbilirubinemia is due to Gilbert's
	syndrome)
AST, ALT	\leq 3 × ULN (<5 × ULN if liver metastases)
Treatment-Related Adverse Event	NCI CTCAE Grade <2 or baseline level (except for alopecia)

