9.2.6 Management of Hematologic Adverse Events Associated with PLD

Participants must have adequate hematological function with no transfusion or colony stimulating factor or erythropoiesis-stimulating agent for at least 2 weeks prior to Cycle 1 Day 1.

Primary prophylactic use of colony stimulating factors or erythropoiesis-stimulating agents or blood product transfusions are not permitted during the first 28 days of Phase 1 Cycle 1 (DLT evaluation period), unless indicated due to medical emergency.

Therapeutic and prophylactic use of G-CSFs is allowed per ASCO and NCCN guidelines. Management of hematologic adverse events associated with PLD administration is described in Table 24.

Table 24. Management of Hematologic Adverse Events Associated with PLD

CTCAE Grade	Management Guidelines
Grade 1 Neutropenia Grade 1 Thrombocytopenia	Resume treatment with no dose reduction
Grade 2 Neutropenia Grade 2 Thrombocytopenia	Hold administration of PLD until the adverse event recovers to Grade ≤1 or to baseline level, then resume treatment with no dose reduction
Grade 3 Neutropenia Grade 3 Thrombocytopenia	Hold administration of PLD until the adverse event recovers to Grade ≤1 or to baseline level, then resume treatment with no dose reduction
Grade 4 Neutropenia Grade 4 Thrombocytopenia	Hold administration of PLD until the adverse event recovers to Grade ≤1 or to baseline level, then resume treatment with first dose reduction

Management should be guided by the more severe toxicity if neutropenia and thrombocytopenia are both observed.

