9.2.7 Management of Hand-Foot Syndrome Associated with PLD

Management of hand-foot syndrome (HFS) associated with PLD administration is described in Table 25.

Table 25. Management of Hand-Foot Syndrome Associated with PLD

CTCAE Grade	Management Guidelines
Grade 1: Mild erythema, swelling, or desquamation not interfering with daily activities	If no previous Grade 3 or Grade 4 HFS: no dose adjustment If previous Grade 3 or Grade 4 HFS: delay dose up to two weeks, then decrease dose by 25%
Grade 2: Erythema, desquamation, or swelling interfering with but not precluding normal physical activities; small blisters or ulcerations less than 2 cm in diameter	 Delay dosing up to two weeks or until resolved to Grade 0 - 1 Discontinue if no resolution after two weeks If resolved to Grade 0 - 1 with two weeks and: no previous Grade 3 or Grade 4 HFS: continue treatment at previous dose previous Grade 3 or Grade 4 toxicity: decrease dose by 25%
Grade 3: Blistering, ulceration, or swelling interfering with walking or normal daily activities; cannot wear regular clothing	Delay dosing up to two weeks or until resolved to Grade 0 – 1, then decrease dose by 25% Discontinue if no resolution after two weeks
Grade 4: Diffuse or local process causing infectious complications, or a bed-ridden state or hospitalization	 Delay dosing up to two weeks or until resolved to Grade 0 – 1, then decrease dose by 25% Discontinue if no resolution after two weeks

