9.3 Management of Adverse Events not Attributable to a Specific Study Treatment

Guidelines for managing adverse events when attribution to either TTI-622 or PLD is not possible in the opinion of the investigator are provided in Table 27. Discussion with the medical monitor is recommended to ensure homogeneity in adverse event management across all participants to the extent possible.

Table 27. General Guidelines for Management of Adverse Events when Attribution is not Possible in the Opinion of the Investigator

Observation	Management Guidelines
 Hematologic Toxicity¹Grade ≥ 3 neutropenia (ANC < 1 x 10°/L) Grade ≥ 3 thrombocytopenia(platelets <50 x 10°/L) Grade ≥ 3 anemia Hemoglobin < 8 g/dL Non-Hematologic Toxicity¹Grade ≥ 3 events excluding: Sub-optimally treated nausea, vomiting, diarrhea Alopecia Transient fatigue of a duration consistent with that associated with doxorubicin 	 First Appearance Delay study treatment until recovery to Grade ≤ 1 or baseline with ANC >1.5 x 10⁹/L and platelets ≥75x 10⁹/L. If no recovery after a delay of >21 days, discontinue PF-07901801 and remove participant from study. First Re-Appearance Delay study treatment until recovery to Grade ≤1 or baseline. If no recovery after a delay of >21 days, discontinuePF-07901801 and remove participant from study. Reduce PF-07901801 dose level by one dose level.
 treatment (1-2 weeks) Infusion-related reaction in the absence of described prophylaxis Laboratory abnormalities that are asymptomatic and/or judged by the investigator as not clinically significant for the patient 	 No change in PLD dose level. Second Re-Appearance Reduce PF-07901801 dose level by one additional dose level. No change in PLD dose level. Third Re-Appearance Reduce PLD dose level by one dose level. No change from previous PF-07901801 dose level.
	Fourth Re-Appearance Reduce PLD dose level by one additional dose level. No change from previous PF-07901801 dose level.
Hematologic Toxicity	No treatment delay
• Grade 1 or Grade 2	No change in dose level
Non-Hematologic ToxicityGrade 1 or Grade 2 1 Interventional or supportive care may be introduced (continuous).	

1 Interventional or supportive care may be introduced (e.g., G-CSF for neutropenia)

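### Table 27 orders dosing to continue at Grade 1–2 for platelet and neutrophil counts that fail the dosing thresholds of Tables 14 and 21

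*Protocol*

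**What the plan says.** Three sets of rules apply to the same blood count.

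- **Dosing thresholds, PF-07901801 (Protocol 9.1.2, Table 14).** "The parameters described in Table 14 should be met for re-treatment with PF-07901801 on any study day". The minimum is 75 × 10^9/L for platelets and 1.0 × 10^9/L for ANC.
- **Dosing thresholds, PLD (Protocol 9.2.2, Table 21).** "The laboratory parameters described in Table 21 should be met for re-treatment with PLD (i.e., initiation of a new cycle"). The minimum is 75 × 10^9/L for platelets and 1.5 × 10^9/L for ANC.
- **Unattributable events (Protocol 9.3, Table 27).** Grade 3 or worse is set at platelets below 50 and ANC below 1 × 10^9/L, and calls for a delay. For Grade 1 or 2 hematologic toxicity the instruction is "No treatment delay", with the dose level unchanged.

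Two further rules bear on these. Table 24 (Protocol 9.2.6) covers Grade 2 neutropenia or thrombocytopenia attributed to PLD: "Hold administration of PLD until the adverse event recovers to Grade ≤1 or to baseline level, then resume treatment with no dose reduction". Section 9.1, repeated in the Synopsis, says that an asymptomatic laboratory abnormality (proteinuria apart) should not interrupt dosing unless the investigator finds it clinically significant or life-threatening.

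**The concern.** Tables 14 and 21 do not depend on attribution. They apply to every participant about to be dosed, including one whose low count cannot be assigned to either drug. For such a participant, Table 27 can say to dose on the same day that Table 14 or Table 21 says not to. Two sites could each follow the protocol and one would dose while the other held.

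The order of caution is also odd. A Grade 2 fall in platelets or neutrophils attributed to PLD leads to a PLD hold under Table 24. If the fall is attributed to PF-07901801, Table 16 starts only at Grade 3 for platelets and Grade 4 for uncomplicated neutropenia, so the Table 14 minimum is what applies. When attribution fails, the protocol gives its least cautious instruction.

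What is at stake is dosing safety and uniform handling between sites, and after that the descriptive summaries of dose delay and dose intensity.

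**Working it through.** The plan states no figure to reproduce here. The check is a comparison of intervals. The Grade 1–2 row of Table 27 is bounded below by that table's own Grade 3 limits, so no outside grading table is needed.

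| Count (× 10^9/L) | Table 27 | Table 14 (PF-07901801) | Table 21 (PLD, new cycle) |
|---|---|---|---|
| Platelets below 50 | delay | fails | fails |
| Platelets 50–74 | no delay | **fails** | **fails** |
| Platelets 75 or more | no delay | passes | passes |
| ANC below 1.0 | delay | fails | fails |
| ANC 1.0–1.49 | no delay | passes | **fails** |
| ANC 1.5 or more | no delay | passes | passes |

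The conflict is confined to two bands: platelets of 50–74 for both drugs, and ANC of 1.0–1.49 for PLD only. Against Table 14 there is no ANC conflict, because its minimum of 1.0 equals Table 27's Grade 3 limit.

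**Table 27 against itself.** After a first Grade 3 or worse event, Table 27 requires platelets of at least 75 and ANC above 1.5 before dosing resumes. A platelet count of 60 therefore blocks dosing when it is recovering from 45, but not when it has just fallen to 60.

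**Effect of the Section 9.1 rule.**
- Suppose it overrides the thresholds. An asymptomatic count not judged significant may then be dosed, in agreement with Table 27. The conflict remains for counts that are symptomatic or judged significant.
- Suppose it does not. The whole of both bands is in conflict.

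The protocol does not say which of these holds.

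**Length of a hold.** In Table 28 the next scheduled hematology is 7 days away in Cycle 1, and in Cycles 2–3 at 48 mg/kg; otherwise it is 14 days away. An unscheduled recheck could shorten this to about 1 day (assumed). SAP 8.2.1 counts a delay of 1–3 days as no delay, so only holds of 4 days or more would show.

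**Dose intensity, illustrative.** SAP 8.1 defines PLD exposure in weeks as (last dose date − first dose date + 28)/7, and the planned PLD dose is proportional to it.
- Four cycles on time: (84 + 28)/7 = 16 weeks.
- Four cycles with one 7-day hold: (91 + 28)/7 = 17 weeks.
- Change in planned dose: 17/16 − 1 = 6.25%.

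The planned PF-07901801 dose is counted by cycle, so an infusion given late within its cycle leaves it unchanged.

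**DLT evaluability.** At 48 mg/kg without loading doses, Cycle 1 has two PF-07901801 infusions and both are needed. A Day 15 infusion held for 7 days falls on Day 22, inside the 28-day window. It is lost only if it is not given by Day 28, which is 28 − 15 = 13 days later.

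**The case against.** The best defence is that the tables can be read together. Tables 14 and 21 are titled as requirements and Table 27 as general guidelines. The natural reading is then that a Grade 1–2 event does not by itself cause a delay, while the dosing-day limits still apply. Table 27's own resumption limits show that its authors had those thresholds in mind. Section 9.1 permits interruption for any count judged significant. Section 9.2 allows alternate PLD modifications after discussion with the medical monitor. Section 9.3 adds: "Discussion with the medical monitor is recommended to ensure homogeneity in adverse event management across all participants".

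Much of this stands, and it is why the point is minor. It does not settle the matter. The titles do not state an order of precedence, and Table 27's instruction at Grade 1–2 is unqualified. The Section 9.1 rule does not mention Tables 14 or 21. Discussion with the monitor is recommended, but no text tells the monitor which rule is the default.

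It can also be argued that the thresholds are only tests for resuming after a hold, as Tables 16 and 17 and Section 5.3 use them. Sections 9.1.2 and 9.2.2 are worded more broadly: any study day for PF-07901801, and the start of a new cycle for PLD.

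A reader might infer a second conflict. The adverse-event row of Table 14 reads "NCI CTCAE Grade <2 or baseline level (except for alopecia"), which would bar dosing at a tolerable Grade 2 event, whereas Table 18 says "Maintain PF-07901801 dose level". The documents do not support pressing this. It rests on one inequality sign, and such signs are not dependable in the available text: the ANC and platelet entry limits carry different signs in the Synopsis and in Section 6.2. If the original allows Grade 2, the conflict disappears. Table 18 speaks of dose level, not of the dosing date. The sentence introducing Table 21 refers to laboratory parameters only.

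**Conclusion.** The conflict on counts is real and narrow. It covers unattributable events with platelets of 50–74 × 10^9/L (Table 27 against Tables 14 and 21) and with ANC of 1.0–1.49 × 10^9/L at the start of a PLD cycle (Table 27 against Table 21). If the Section 9.1 rule is taken to override the thresholds, it shrinks to counts in those bands that are symptomatic or judged clinically significant.

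The documents give no frequency for these bands. The monotherapy study reports related thrombocytopenia in 9 of 43 participants (21%) and related neutropenia in 5 of 43 (12%), at any grade and doses up to 18 mg/kg. Low counts are therefore to be expected, but those figures do not say how many would fall in the bands or be unattributable.

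The 6.25% is what any single 7-day PLD hold would do over four cycles. It illustrates a delay and does not estimate the effect of this conflict. Nobody should infer that the efficacy conclusion is at risk: the threshold of six responses in 25 and the sample size do not depend on these tables. Severity is minor, and the case for a correction rests on dosing safety and consistency.

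**What to change.** 1. Add to the Grade 1–2 row of Table 27 that the laboratory thresholds of Table 14 (for PF-07901801) and Table 21 (for PLD) must still be met on the dosing day.
2. Add one sentence stating that these specific thresholds take precedence over the general asymptomatic-laboratory rule in Section 9.1 and the Synopsis. If the sponsor intends the reverse, say that instead.

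The adverse-event grade row of Tables 14 and 21 needs no change on this account. Loosening it would move Table 21 towards the less cautious rule.

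The cost is a wording amendment, with no change to the sample size, visit schedule or data collection. The downside is a few more short holds, which an early recheck of the count can limit.

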9.1.3 PF-07901801 Dose Modification Guidelines

Table 15 describes modifications for the dose levels intended to be evaluated in the dose escalation portion of the study.

Table 15. PF-07901801 Dose Modifications

Dose Level	Dose Level -1	Dose Level -2
48 mg/kg	32 mg/kg	24 mg/kg
24 mg/kg	18 mg/kg	12 mg/kg
12 mg/kg	8.0 mg/kg	4.0 mg/kg

While PF-07901801 has demonstrated clinical activity in Study TTI-622-01 at dose levels as low as 0.8 mg/kg, the agent has demonstrated a very promising safety profile suggesting that dose reductions may not be routinely required. Thus, the study does not prospectively envision

requirement for a dose level below 4.0 mg/kg but a lower dose level may be allowed after consultation with the sponsor medical monitor for a participant who is receiving disease control and remaining on treatment is, in the opinion of the investigator, a reasonable treatment option for the participant.

9.1.4 Hematologic Adverse Events Related to PF-07901801 Administration

Blood counts will be monitored regularly as outlined in the Schedule of Assessments, Table 28 in Section 10, with additional testing obtained according to standard clinical practice. Management of hematologic adverse events associated with PF-07901801 administration is summarized in Table 16, Management of Hematologic Adverse Events Associated with PF-07901801 Platelet transfusion is allowed to manage thrombocytopenia to prevent and minimize bleeding according to ASH and ASCO guidelines. Per these guidelines, the platelet count threshold for prophylactic platelet transfusion is $<10,000 \times 10^9/L$. Investigators should consider the participant's medical history, concomitant medications and concurrent conditions to provide support for thrombocytopenia.

Table 16. Management of Hematologic Adverse Events Associated with -PF-07901801 Administration

Observation	Management Guidelines
Grade 3 thrombocytopenia Grade 4 thrombocytopenia lasting ≤72 hours	• Continue PF-07901801 at the same dose when the re-treatment criterion (≥75 x 10 ⁹ /L or baseline) is met
Grade 4 thrombocytopenia lasting >72 hours $Platelets \leq 10 \times 10^9/L \ at \ any \ time$	 Delay PF-07901801 dosing until the re-treatment criterion (≥75 x 10⁹/L or baseline) is met Transfuse platelet prophylactically against bleeding when platelets ≤10 × 10⁹/L per ASCO practice guideline, then resume PF-07901801: At the same dose if dose delay was ≤1 week One dose level reduction if dose delay was >1 week One dose level reduction if the event recurs
Grade ≥3 thrombocytopenia with clinical bleeding (more than easily-controlled epistaxis, mild gum bleeding or menses) Grade 4 neutropenia lasting >72 hours	Delay PF-07901801 dosing until the re-treatment criterion (≥75 x 10 ⁹ /L or baseline) is met and then resume PF- 07901801 at a reduced dose (1 dose level reduction) • Delay PF-07901801 dosing until the re-treatment criterion (ANC >1.0 × 10 ⁹ /L) is met, then resume PF-07901801: • At the same dose if dose delay was ≤1 week • One dose level reduction if dose delay was >1 week • One dose level reduction if the event recurs

Table 16. Management of Hematologic Adverse Events Associated with -PF-07901801 Administration

Observation	Management Guidelines
